3.2. Run-In Phase

3.2.1 Screening Evaluations

The following procedures/assessments will be performed during the screening visit, which will be performed within 28 days prior to Day 1 of Cycle 1:

- Written informed consent
- Review of inclusion and exclusion criteria
- Initial history and pre-existing conditions
- Human Papillomavirus (HPV) status
- Historic illnesses
- Physical examination
- Vital signs
- Eastern Cooperative Oncology Group (ECOG) performance status
- AEs
- Concomitant medication
- 12-lead ECG
- Tumor measurement
- Radiological imaging according to RECIST
- Dynamic contrast-enhanced magnetic resonance imaging (DCE-MRI)
- Urinalysis
- EORTC QLQ-C30 and H&N35
- Laboratory tests (hematology, clinical chemistry and serum pregnancy test)
- Nerve Conduction Velocity (within 30 days before C1D1 for all subjects.)

3.2.2 Cycle 1, Day 1 (C1D1)

The following procedures/assessments will be performed:

- Review of inclusion and exclusion criteria
- Physical examination
- Vital signs
- Calculation of body surface area (BSA)
- ECOG performance status
- AEs
- Concomitant medication
- 12-lead ECG
- Urinalysis*
- Laboratory tests (hematology*, clinical chemistry* and coagulation)
- Study treatment infusion
- PK sampling
- Collection of blood samples for biomarkers (vascular endothelial growth factor [VEGF], circulating endothelial cells [CEC] and circulating endothelial progenitor [CEP] cells).
- DCE-MRI

*Test results within 7 days are acceptable, only items not performed for screening within 7 days before this visit need to be tested again.

- Study Drug Administration

3.2.3 Cycle 1, Day 8 (C1D8) ±1 day

The following assessments will be performed:

- Physical examination
- Vital signs
- Calculation of BSA
- ECOG performance status
- AEs
- Concomitant medication
- 12-lead ECG
- Laboratory tests (hematology, clinical chemistry and coagulation)
- Study treatment infusion
- EORTC QLQ-C30 and H&N35
- PK sampling
- Study Drug Administration

3.2.4 Cycle 1, Day 15 (C1D15) ±2 days

The following assessments will be performed:

- Physical examination
- Vital signs
- ECOG performance status
- AEs
- Concomitant medication
- Laboratory tests (hematology, clinical chemistry and coagulation)
- EORTC QLQ-C30 and H&N35

3.2.5 Cycle 2, Day 1 (C2D1) ±1 day

The following assessments will be performed:

- Physical examination
- Vital signs
- Calculation of BSA
- ECOG performance status
- AEs
- Concomitant medication
- 12-lead ECG
- Urinalysis
- Laboratory tests (hematology, clinical chemistry and coagulation)
- Study treatment infusion
- EORTC QLQ-C30 and H&N35
- PK sampling
- Study Drug Administration

3.2.6 Cycle 2, Day 8 (C2D8) ±1 day

The assessments on Day 8 of Cycle 2 is identical to Cycle 1, Day 8 (see Section 3.2.3 above)

3.2.7 Cycle 2, Day 15 (C2D15) ±2 days

The assessments on Day 15 of Cycle 2 is identical to Cycle 1, Day 15 (see Section 3.2.4 above)

3.2.8 Cycle 3, Day 1 (C3D1) ±1 day

The assessments on Day 1 of Cycle 3 are identical to Cycle 2, Day 1 (see Section 3.2.5 above).

3.2.9 Cycle 3, Day 8 (C3D8) ±1 day

The assessments on Day 8 of Cycle 3 is identical to Cycle 1, Day 8 and Cycle 2, Day 8 (see Section 3.2.3 above)

3.2.10 Cycle 3, Day 15 (C3D15) ±2 days

The assessments on Day 15 of Cycle 3 is identical to Cycle 1, Day 15 and Cycle 2, Day 15 (see Section 3.2.4 above) and also includes collection of blood samples for biomarkers (VEGF, CEC and CEP)

3.2.11 3.2.11 Cycle 4, Days 1 and 8 (C4D1 and C4D8)

Patients may continue with treatment of SCB01A at the same dose per investigator discretion if the patient is experiencing clinical benefit, until the study is terminated. The assessments on Days 1 and 8 will continue to be the same as for Cycle 2, Day 1 and Day 8 (see Sections 3.2.5) with the exception that no PK sampling will be performed.

Tumor assessment should be performed at baseline, and at the end of every 3 cycles which needs to be arranged within 5 days prior to the next cycle.

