¹ Patients may continue treatment beyond 3 cycles (9 weeks) of SCB01A treatment per investigator discretion if they are experiencing clinical benefit, until the study is terminated.

² EOT visit should be conducted 21 \pm 2 days after the last infusion. Early withdrawal visit should be conducted within 21 days after the patient received the last dose of study treatment.

³ Follow-up visits will be performed after the patient completes EOT visit or early withdrawal visit. Follow-up visits will be scheduled every 3 weeks for 9 weeks, thereafter every 9 weeks until the end of the study. These visits can be conducted by phone.

⁴ Starting from cycle 4, there will be no study visit on Day 15.

⁵ All AEs including SAEs must be reported from the time of informed consent signed and must continue to be followed for 28 days after last administration of study treatment.

⁶ ECG will be performed prior to study drug administration, within 1 hour following study drug administration, 2 hours after study drug administration, immediately after the 3 hour infusion, 4 hours after study drug administration, and 24 hours after administration of the study drug. Starting from Cycle 4, the ECG will be obtained at every treatment cycle within 1 hour following study drug administration and at EOT/early withdrawal visit (time window: ± 5 min).

⁷ Tumor assessments should be performed at baseline, and every 3 cycles prior to next cycle until progression of disease. For patients who meet DC criteria after the first 3 cycles of study treatment, additional radiological tumor assessments should be performed at Week 12. Any additional assessment can be arranged when clinically indicated.

⁸ Test results within 7 days prior to Cycle 1, Day 1 (C1D1) are acceptable. Only items not performed or obtained within 7 days prior to C1D1 should be tested.

⁹ Serum pregnancy test for women of childbearing potential must be performed ≤ 14 day prior to first dose.

¹⁰ Quality of Life questionnaires (EORTC QLQ-C30 and H&N35) should be performed at Screening and all clinic visits (before study drug administered, where applicable, except at C1D1).

¹¹ Blood Sample for VEGF and CEC will be taken immediately pre-infusion then at 6, 10 and 24 hours after start of infusion on C1D1 and C3D15. Blood Samples for CEP will be taken immediately pre-infusion and C3D15.

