Two phase I clinical studies were performed “A Phase 1 Dose Escalation Study of SCB01A in Subjects with Advanced Solid Tumors Who Have Failed Standard Therapy” and “Long-Term Compassionate Use Study for Continued Administration of SCB01A in Subjects Who Completed Treatment With SCB01A in the Previous Protocol #SCB01A-01” respectively. The phase I study demonstrated that SCB01A has encouraging safety and efficacy and support for further Phase II study. 33 subjects were enrolled in the study and 31 subjects completed the main treatment. Among the 31 subjects, 11 of them completed the extension treatment of SCB01A. Up to date, 5 subjects, two in main and extension period respectively, experienced 7 SUSAR events. (Including gastric ulcer bleeding, thrombocytopenia, cough, radiation recall dermatitis and thromboembolic event, Muscle weakness lower limb and Sepsis). In addition, 5 dose limiting toxicities and 61 adverse reactions were reported in this study.

The aim of this Phase II study with SCB01A is to determine the effect of SCB01A in patients with squamous cell carcinoma of head and neck who have failed previous platinum based therapies.

2. Study Objectives

2.1. Run-In Phase:

Primary Objective

To determine the optimal dose for 3 cycles of i.v. administration of SCB01A on Days 1 and 8 of each cycle in a 3-week cycle.

Secondary Objective:

To evaluate the safety and toxicity for 3 cycles of i.v. administration of SCB01A on Days 1 and 8 of each cycle in a 3-week cycle

2.2. Phase II:

Primary Objective:

To assess the disease control rate (DCR) at the end of the 9th week (3 cycles, each cycle consists of 21 days) after treatment with SCB01A, according to the Response Evaluation Criteria in Solid Tumors (RECIST) version 1.1.

Secondary Objectives

The secondary objectives of the study are listed below:

- To assess the overall survival rate at 36 weeks after treatment of SCB01A in patients with recurrent or metastatic squamous cell head and neck cancer who have previously been treated with platinum therapy.
- To assess the progression-free survival (PFS)
- To determine the recommended dose regimen of SCB01A for further investigation in different settings of head and neck squamous cell cancer.
- To assess the safety and toxicity profile of study treatment.
- To assess the PK profile of SCB01A of patients in the run-in phase.

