4.9. Dose Adjustment and Toxicity Management

There is no dose adjustment envisaged in this study. Where a study treatment-related Grade 3 or 4 AE occurs, the study treatment will be placed on hold until the event is resolved to grade ≤ 1 or returns to baseline before resuming the study drug. If the Grade 3 or 4 event does not resolve or return to baseline within 14 days or return to grade 3 or 4 toxicity after resuming, treatment with the study drug will cease. However the patient should be followed-up for survival analysis until the end of the study.

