6.1. Efficacy Measurements

Tumor response will be assessed by using computerized tomography (CT) or MRI scans according to RECIST v1.1 at baseline, and every 3 cycles prior to next cycle until progression of disease. For patients who meet DC criteria after the first 3 cycles of study treatment, additional radiological tumor assessments should be performed at Week 12. Any additional assessments can be arranged when clinically indicated.

Scans must include brain, chest, abdomen, and pelvis. The imaging technique used at baseline should be used throughout the study.

Survival data will be collected throughout the active treatment phase and during the follow-up period. Survival follow-up after patient discontinuation of treatment will be conducted every 3 weeks during the first 9 weeks, thereafter every 9 weeks until the end of the study. Survival rate will only be assessed in patients with measurable disease at baseline.

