10.1. Tumor Response and Disease Control Rate

Tumor assessments were made based upon the RECIST criteria (Response Evaluation Criteria in Solid Tumors version 1.1). Tumor assessments were scheduled at baseline, and every 3 cycles prior to next cycle until progression of disease. For this analysis purpose, tumor response evaluation at Week 9 (Cycle 4, Day 1) or end of treatment/early termination will be pooled and used as the best overall response from start of dosing up to Week 9.

For the analysis of tumor response, a summary table presenting the number and proportion of responders (DC) and non-responders (non-DC) in each dose level, together with the two-sided 90% and 95% confidence intervals for response rates will be produced. The proportion and the corresponding 90% and 95% confidence interval for each of the response categories (CR, PR, SD, PD, and unevaluable) by dose level will also be presented. The confidence interval will be based on Pearson-Clopper exact CI.

The details of target lesions, non-target lesion, and new lesions (if any) will be listed for each subject.

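### Disease control is defined at calendar Week 9 but scans are timed by completed cycles, and neither document says which timing governs once a cycle is delayed

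*Protocol*

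**What the plan says.** **Endpoint.** Protocol 2.2 sets the Phase II primary objective as DCR "at the end of the 9th week (3 cycles, each cycle consists of 21 days"). The synopsis and SAP 2.3 also place DCR at Week 9.

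**Scan timing.** Protocol 3.2.11, in the run-in section, schedules scans "at the end of every 3 cycles which needs to be arranged within 5 days prior to the next cycle". Section 6.1 and footnote 7 of Tables 1 and 2 carry the same cycle-based rule, "every 3 cycles prior to next cycle until progression of disease", and Table 2 is the Phase II schedule. The one scan fixed to the calendar in words is an extra scan at Week 12 for patients with disease control after three cycles.

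**Nominal day.** Tables 1 and 2 place the first on-treatment imaging in the C4D1–CXD1 column, headed Day 64 (±1).

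**Holds.** Section 4.9 holds treatment after a related Grade 3 or 4 event until recovery. Treatment ceases "If the Grade 3 or 4 event does not resolve or return to baseline within 14 days", and also if Grade 3 or 4 toxicity comes back after resuming.

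**SAP.** Section 10.1 uses the "tumor response evaluation at Week 9 (Cycle 4, Day 1"), pooled with the end-of-treatment or early-termination evaluation. It gives no day window.

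**The concern.** The calendar and the cycle count agree only if all three cycles last exactly 21 days. Section 4.9 allows them to run longer, and delays are a planned summary (synopsis safety measurements; SAP 8).

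After a delay, the primary assessment is made later in some patients than in others. A patient controlled at Week 9 who progresses by Week 11 counts as a success if treated on time, but as a failure if delayed. For PFS the effect is reversed: progression is dated by the scan that shows it, so a later scan lengthens PFS. Delays under 4.9 follow from toxicity, so both effects depend on toxicity and could differ by dose. DCR would then no longer be purely the Week 9 quantity for which 10% and 25% were specified.

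**Working it through.** **1. Reproduce the design.** Inputs from Protocol 8.2: p0 = 0.10, p1 = 0.25, one-sided alpha 10%, power 80%. Rule from the synopsis and SAP 2.1: stop if 1 or fewer of 13 have disease control; success needs at least 6 of 34. (Protocol 8.2, 8.5 and 8.8 give a different stage 1 boundary. That is a separate matter; the rule used here is the one that reproduces the stated design.)

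P(success | p) = Σ over x from 2 to 13 of P(X1 = x) · P(X2 ≥ 6 − x), with X1 ~ Bin(13, p) and X2 ~ Bin(21, p).

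- p = 0.10: alpha = 9.6%
- p = 0.25: power = 81.1%

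A search over two-stage designs returns this as the Simon optimal design, so N = 34 is confirmed.

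**2. Scan day.** Undelayed C4D1 is 3 × 21 + 1 = Day 64. A scan in the 5 days before it, or on the day, falls on Days 59–64, that is (59 − 1)/7 = 8.3 to (64 − 1)/7 = 9.0 weeks after first dose. A 14-day shift gives Days 73–78, or 10.3 to 11.0 weeks.

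**3. Disease control at a later scan.** Assume a constant progression hazard through the plan's Week 9 values, so DC(t) = p^(t/63) with t in days from first dose.

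- 7-day shift (70 days): 0.25 becomes 0.214; 0.10 becomes 0.077
- 14-day shift (77 days): 0.25 becomes 0.184; 0.10 becomes 0.060

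**4. Operating characteristics.** If a share f of patients is shifted, the average probability is (1 − f)·p + f·DC(t). Example, f = 0.20 and 14 days: 0.8 × 0.25 + 0.2 × 0.184 = 0.237. Inserting these averages in step 1:

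| Share shifted | Power, 7 days | Power, 14 days | Alpha, 14 days |
|---|---|---|---|
| 0% | 81.1% | 81.1% | 9.6% |
| 10% | 80.0% | 79.0% | 8.2% |
| 20% | 78.9% | 76.8% | 7.0% |
| 30% | 77.7% | 74.4% | 5.9% |
| 40% | 76.5% | 71.9% | 4.9% |

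**5. Hazard shape.** With 30% shifted by 14 days, Weibull shapes 0.5 and 1.5 give power 77.9% and 70.9%, against 74.4% for the constant hazard.

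**The case against.** **The tables already give Day 64.** They do, so it would be wrong to say that no scan is planned near Week 9. But the same column serves C4D1 and every later Day 1, so its day is nominal, and no text says that it overrides the cycle rule after a delay.

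**Not every hold moves the scan.** This stands. A hold that ends before the next due dose changes nothing, and an omitted dose, which the synopsis and SAP 8 list separately from a delay, leaves C4D1 in place. The protocol does not say when a held dose is delayed and when it is omitted. The Week 12 scan is fixed to the calendar and does not move.

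**Repeated holds.** A reader might infer that two 14-day holds would put the scan at Week 13, and that the Week 12 scan could then precede the result that triggers it. The documents do not support building on this. Section 4.9 also ends treatment if Grade 3 or 4 toxicity returns after resuming, so a second hold would need a different toxicity and a narrow reading of that clause. One full hold reaches about Week 11, still before Week 12.

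**Size.** The hold rate, hold length and hazard are all assumed. At 10% shifted, the power loss is about 1 to 2 points. Type I error falls as well, so delay alone does not raise the false-positive risk.

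**Practical effect.** SAP 1 states that the trial stopped in run-in with five enrolled and none in Phase II. The power loss therefore cannot arise in the data to be analysed, and SAP 10 makes efficacy primarily descriptive. However, the DCR and PFS tables (14.2.1.1 and 14.2.1.2) are still marked for generation.

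**Conclusion.** The point holds in a limited form. The endpoint runs on the calendar, the routine scans run on cycles, and neither document says which governs after a delay or gives a window for the Week 9 scan. A hold that shifts the cycles can move the primary assessment by up to 14 days, to about Days 73–78. In delayed patients this makes disease control harder to achieve and dates progression later.

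That timing follows from the documents' own figures. The power figures do not: they are illustrations resting on an assumed share of delayed patients, an assumed shift and a constant hazard. Within the range shown, power is 80.0% to 71.9% against 81.1% with no delay, with a lower type I error. For the trial as it ended, the live part is the undefined Week 9 window in SAP 10.1.

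**What to change.** **Protocol.** In 3.2.11, 6.1, the synopsis and footnote 7 of Tables 1 and 2, time tumour assessments from C1D1: Week 9 at the tables' own Day 64 with a stated window, Week 12 for patients with disease control, then every 9 weeks until progression. State that these dates hold regardless of cycle delays. Nothing in the dosing or hold rules needs to change for this.

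**SAP.** In 10.1, replace the equation of Week 9 with Cycle 4 Day 1 by the same calendar window.

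**Cost.** An amendment and SAP wording, with essentially the same number of scans for patients on treatment. The downside is that a scan may fall mid-cycle for a delayed patient. With recruitment over, only the SAP change bears on the planned DCR table.

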3.3. Phase II

During Phase II, Optimal Dose will be administered depending on the decision made by the safety committee. The Optimal Dose decided by safety committee, will be infused on Days 1 and 8 of each 3-week cycle as for the run-in phase. There will be no PK assessments to be performed in this phase.

3.3.1 Screening Evaluations

The screening procedures/assessments will be performed within 28 days prior to Day 1 of Cycle 1 and are identical to the screening assessments performed before the run-in phase (see Section 0.1).

3.3.2 Cycle 1, Day 1 (C1D1) (Optimal Dose))

The following assessments will be performed:

- Review of inclusion and exclusion criteria
- Physical examination
- Vital signs
- Calculation of BSA
- ECOG performance status
- AEs
- Concomitant medication
- 12-lead ECG
- Urinalysis*
- Laboratory tests (hematology*, clinical chemistry* and coagulation)

- Study treatment infusion
- DCE-MRI

*Test results within 7 days are acceptable, only items not performed for screening within 7 days before this visit need to be tested again.

- Study Drug Administration

3.3.3 Cycle 1, Day 8 (C1D8) ±1 day (Optimal Dose)

The following assessments will be performed:

- Physical examination
- Vital signs
- Calculation of BSA
- ECOG performance status
- AEs
- Concomitant medication
- 12-lead ECG
- Laboratory tests (hematology, clinical chemistry and coagulation)
- Study treatment infusion
- EORTC QLQ-C30 and H&N35
- Nerve Conduction Velocity
- Study Drug Administration

3.3.4 Cycle 1, Day 15 (C1D15) ±2 days (Optimal Dose)

The following assessments will be performed:

- Physical examination
- Vital signs
- ECOG performance status
- AEs
- Concomitant medication
- Laboratory tests (hematology, clinical chemistry and coagulation)
- EORTC QLQ-C30 and H&N35

3.3.5 Cycle 2, Day 1 (C2D1) ±1 day (Optimal Dose)

The following assessments will be performed:

- Physical examination
- Vital signs
- Calculation of BSA
- ECOG performance status
- AEs
- Concomitant medication
- 12-lead ECG
- Urinalysis

- Laboratory tests (hematology, clinical chemistry and coagulation)
- Study treatment infusion
- EORTC QLQ-C30 and H&N35
- Study Drug Administration

3.3.6 Cycle 2, Day 8 (C2D8) ± 1 day (Optimal Dose)

The assessments on Day 8 of Cycle 2 is identical to Cycle 1, Day 8 (see Section 3.3.3 above)

3.3.7 Cycle 2, Day 15 (C2D15) ± 2 days (Optimal Dose)

The assessments on Day 15 of Cycle 2 is identical to Cycle 1, Day 15 (see Section 3.3.4 above)

3.3.8 Cycles >2 , Day 1 ± 1 day (Optimal Dose)

The assessments on Day 1 of Cycles >2 are identical to Cycle 2, Day 1 of Phase II (see Section 3.3.5 above).

3.3.9 Cycles >2 , Day 8 ± 1 day (Optimal Dose)

The assessments on Day 8 of Cycles >2 are identical to Cycle 1, Day 8 of Phase II (see Section 3.3.3 above).

3.3.10 Cycles >2 , Day 15 ± 2 days (Optimal Dose)

The assessments on Day 15 of Cycle 2 is identical to Cycle 1, Day 15 (see Section 3.3.4 above)

3.4. End of Treatment (EOT) Evaluation/Early Withdrawal

EOT visit should be conducted 21 ± 2 days after the last infusion. Early withdrawal visit should be conducted within 21 days after the patient receives the last dose of study treatment.

The following assessments will be performed at the EOT/early withdrawal visit:

- Physical examination
- Vital signs
- ECOG performance status
- AEs
- Concomitant medication
- 12-lead ECG
- Tumor assessment (radiological imaging)
- Urinalysis
- Laboratory tests (hematology, clinical chemistry and coagulation)
- EORTC QLQ-C30 and H&N35

3.5. Follow-up

After discontinuation of study treatment, all patients will be followed for survival and disease-specific therapies of the clinician's choice will be administered. The data will be collected and can be done by telephone. Follow-up visits will be scheduled every 3 weeks for 9 weeks, thereafter every 9 until the end of the study.

3.6. Unscheduled Visit

The following assessments will be performed during an unscheduled visit:

- Physical examination
- Vital signs
- ECOG performance status
- AEs
- Concomitant medication
- 12-lead ECG*
- Tumor assessment (radiological imaging)*
- Urinalysis*
- Laboratory tests (hematology, clinical chemistry and coagulation)

*To be performed when necessary at the patient's request or per Investigator decision.

3.7. Study Design, Including the Choice of Control Groups

There is no control group in this Phase II study. The rationale for the study is discussed in Section 1.2.

3.8. Selection of Study Population

3.8.1. Inclusion Criteria:

1. Aged \geq 20 years;
2. Signed informed consent obtained prior to initiation of any study-specific procedures and treatment;
3. Histological or cytological confirmed squamous cell carcinoma of head and neck;
4. Patients with non-resectable, unfeasible radiotherapy, recurrent or metastatic head and neck squamous cell carcinoma, after previous treatment with platinum agent;
5. At least one measurable tumor lesion as defined by RECIST version 1.1 as assessed by the investigator (local radiological image assessment);
6. Eastern Cooperative Oncology Group (ECOG) Performance Status (PS) 0-2;
7. Life expectancy of 12 weeks or longer;
8. Patients must have radiological measurable or clinically evaluable disease. Physical examination and radiographic studies have to be performed within 28 days of enrolment;
9. Concurrent local therapy is not allowed, but concurrent palliative radiation

therapy to non-measurable sites of disease such as painful bone metastasis is permitted;

10. All eligible patients of childbearing potential have to use effective contraception; that is, double barrier contraceptive methods;
11. Documented progressive disease within past 6 months;
12. Adequate bone marrow reserve, cardiac, renal and liver function:
 - a. Absolute neutrophil count (ANC) $> 1.5 \times 10^9/L$;
 - b. White blood cell (WBC) $> 3 \times 10^9/L$
 - c. Platelet count $> 75 \times 10^9/L$;
 - d. Hemoglobin $> 9 \text{ g/dL} (> 5.6 \text{ mmol/l})$;
 - e. Prothrombin time (PT)/international normalized ratio (INR) $\leq 1.5 \times$ upper limit of normal (ULN)
 - f. Creatinine clearance (Cockcroft & Gault formula) $> 50 \text{ mL/min}$;
 - g. Alanine aminotransferase (ALT, SGPT) and aspartate aminotransferase (AST, SGOT) and Alkaline Phosphatase (ALP) $< 3 \times \text{ULN}$.
 - h. Serum albumin $\geq 3 \text{ g/dL}$;
 - i. INR $\leq 1.5 \times \text{ULN}$
 - j. Total Bilirubin $\leq 1.5 \times \text{ULN}$

3.8.2. Exclusion Criteria:

1. Known primary CNS malignancy or CNS involvement (except for brain metastases that have been treated and are stable and patient is off steroids);
2. Chemotherapy, radiation therapy, major surgery or investigational agents less than 4 weeks prior to study drug treatment;
3. History of malignancy other than head and neck cancer. Second primary head and neck tumors are excluded with the exception of early stage non-melanoma skin cancer or carcinoma *in situ* of cervix;
4. Ultrasound or radiological evidence of liver cirrhosis;
5. Severe pulmonary obstructive or restrictive disease;
6. Uncontrolled inflammatory disease (autoimmune or infectious);
7. Clinically significant cardiac disease (NYHA class > 2);
8. Other serious illness or medical conditions, such as active infection, unresolved bowel obstruction, or psychiatric disorders;
9. Known HIV positivity;
10. Participation in another clinical trial or treatment with any investigational drug within 30 days prior to study entry;
11. QTc $> 450 \text{ msec}$;
12. Pregnant or breast-feeding patients, and men and women of child-bearing potential not using effective contraception while on study treatment; Known hypersensitivity to any component of SCB01A;
13. History of exposure to SCB01A or its analogues;
14. History of active or significant neurological disorder or psychiatric disorder that would prohibit the understanding and giving of informed consent, or

would interfere with the clinical and radiological evaluation of central nervous system during the trial;

15. Any other reason the investigator deems the patient to be unsuitable for the study.

